6.1.7 Prior and Concomitant Medications and Blood Products

Instituto Grifols, S.A. / Protocol IG1407

Prior (within 30 days prior to screening) and concomitant medications were required to be recorded in the eCRF. Prior medications and concomitant medications will be summarized separately either overall and by treatment (prior medications) and by treatment group (concomitant medications).

Prior medications are defined as any medication that ended with end date/time prior to the start of study randomization/treatment day 1 for both treatment groups.

Concomitant medications are defined as medications with start date / time on or after the subject's date / time of randomization for SMT group, or commencement of plasma exchange for SMT+PE-A 5% group. In addition, medications with start date / time prior to subject's date / time of randomization/treatment Day 1, and end date/time either ongoing or after subject's date / time of randomization/treatment Day 1 will also be deemed as a concomitant medication.

Prior and concomitant blood products are defined in the same manner.

The following conservative imputation rules will be used for missing or partial end date / time information in order to determine whether a medication is prior or concomitant (i.e., the unknown portions of a medication end date / time will be assumed to be as late as possible):

- Note: year is required on the eCRF, except for ongoing medication
- If the entire end year, date, and time values are missing (i.e., ongoing medication), then no imputation is performed, and the medication will be assigned to the "concomitant" category
- If the month is missing, impute "December"
- If the day is missing, impute the last day of the month (i.e., "28/29/30/31" depending on the year and month)
- If the hours are missing, impute "23"
- If the minutes are missing, impute "59"

The imputed medication end date / time will then be compared with the start of study treatment to determine if the medication is prior or concomitant. Note: it is possible that the imputed end date / time could be assigned to be later in time than the data lock.

Note the imputed end date / time will only be used to determine whether a medication is prior or concomitant. The start / end dates / times reported on the eCRFs will be presented in the listings.

6.2 Sample Size

Based on the CANONIC study, the overall 90-day mortality rate is assumed to be about 50% in the whole study population ([3](#), [6](#)). Assuming a potential drop-out rate of 10% and 5% type-1 error for a 2-sided Chi-square test, a global sample size of 380 subjects (190 per treatment group) will allow an 80% statistical power to detect an absolute reduction of 15% (a 35% 90-day mortality rate) in subjects treated with SMT+PE-A 5%.

Alternatively, the sample size was calculated based on the log-rank test as follows. Assuming the 90-day mortality rate is 50% for the control group, or equivalently, the survival rate is 50%, which translates to a hazard rate of 0.0077 assuming an exponential distribution. Using a log-rank test at the two-sided significant level of 5%, a total of 141 events would provide at least 80% power to detect an absolute reduction of 15% in mortality rate (a 35% 90-day mortality rate, or equivalently, a 65% survival rate) in subjects treated with SMT+PE-A 5%. This absolute difference in mortality rates translates to a hazard ratio of 0.6215, or an approximate 38% risk reduction. With all subjects followed for the entire 90-day duration of the study, a total of 332 subjects would be required to obtain 141 events. Assuming a dropout rate of 10%, a global sample size of 370 subjects (185 per treatment group) is required. This sample size calculation was performed using Proc Power with the "Twosamplesurvival" statement in SAS version 9.4.

Taking a conservative approach, the larger of the 2 sample sizes (i.e., the one based on the Chi-square test) will be used to ensure the study has sufficient power.

6.3 Randomization and Blinding

This is an open-label study. Randomization will be stratified by region (EU or NA) and the 3 ACLF grades (ACLF-1b, ACLF-2, or ACLF-3a). Within each stratum (i.e., each unique combination of region and ACLF grade), subjects will be randomly assigned to 1 of the 2 treatment groups (SMT vs. SMT+PE-A 5%) in a 1:1 ratio. Randomization will be centralized and will be performed via an Interactive Web Response System (IWRS) system after subject inclusion. A computer-generated randomization list will be used for treatment allocation.

6.4 Analysis Populations

There will be 3 analysis populations in this study, Intent-to-Treat (ITT) and Per Protocol (PP) population cohorts are for efficacy assessment and Safety population is for safety evaluation.

6.4.1 Safety Population

The Safety population is defined for the SMT + PE-A 5% treatment group as the subset of subjects who received at least one PE-A 5% treatment; and is defined for the SMT alone treatment group as all subjects randomized to SMT, assuming that all subjects in the SMT arm received the SMT treatment. Safety analyses will be based on this population. Subjects will be grouped according to the treatment they actually received in all safety analyses.

6.4.2 Intent-to-Treat (ITT) Population

The ITT population is defined as subjects who are randomized. The ITT population will be used for all efficacy analyses. Subjects will be grouped according to the treatment to which they are randomized in all efficacy analyses.

6.4.3 Per Protocol (PP) Population

The primary efficacy analyses will be repeated using the per-protocol (PP) population in order to confirm the results based on the ITT population. The PP population includes all subjects in the ITT Population who meet the following criteria:

- 1) For SMT+PE-A 5% group:
 - Subject randomized to SMT+PE-A 5% receives at least the first 2 PE-A 5% sessions
 - Subject has no major protocol violations which might have an impact on the primary efficacy analysis.
- 2) For SMT alone group:
 - Subject randomized to SMT survives more than 2 days following randomization
 - Subject has no major protocol violations which might have an impact on the primary efficacy analysis.

6.5 Hypothesis Testing and Multiplicity Adjustments

All statistical tests will be two-sided with significance level fixed at 0.05.

The fixed-sequence testing method will be used to adjust for multiplicity in the analyses of the secondary efficacy endpoints (using ITT population). Specifically, the superiority of SMT+PE-A 5% versus SMT alone for the secondary efficacy endpoints will only be tested if the superiority for the primary efficacy endpoint is demonstrated at the two-sided significance level of 5% (using ITT population).

Instituto Grifols, S.A. / Protocol IG1407

For the secondary efficacy endpoints, each subsequent hypothesis is tested only if the superiority for the previous comparison(s) has been demonstrated at a two-sided significance level of 5%. The order in which the null hypotheses will be tested is predetermined for the secondary efficacy endpoints as follows:

1. Time to transplant or death through Day 90 after randomization of SMT+PE-A 5% versus SMT alone
2. Time to death through Day 28 after randomization SMT+PE-A 5% versus SMT alone

No other adjustments for multiplicity are planned. P-values will be displayed for all the above pre-specified tests for completeness; interpretation and reporting of significant hypothesis test results will follow the fixed sequence approach described.

7 Subject Disposition and Demographics

Unless otherwise noted, all demographics listings and summaries will be based on the ITT population.

7.1 Subject Disposition

Subject disposition will include the number of all subjects screened, screen failures, number and percentage of subjects in each analysis population including the ITT population, Safety population, and PP population.

The number and percentage of subjects in the ITT population who discontinue from the study will be summarized by reason for discontinuation.

Disposition status will be listed for all subjects, including those who were screened but not randomized.

7.2 Protocol Deviations

Deviations from the protocol will be identified during the study and evaluated before the database lock. Protocol deviations will be listed and will include category, severity (i.e. minor, major, or critical), and description of deviation. Summaries of incidences of deviations and subjects experiencing deviations will be presented for the following: any deviation, critical deviations, major deviations and deviations related to COVID-19.

7.3 Demographics

Demographics (age, sex, race, and ethnicity), baseline weight, and stratification factors for randomization will be listed and summarized. Subjects who were incorrectly stratified at the time of randomization will be listed and summarized.

Baseline characteristics listed above will be compared to evaluate possible imbalance by using Student's t test for continuous variables, Chi-square test for binomial or nominal variables, and Poisson model for count variables (with adjustment for overdispersion). All demographic and baseline characteristics data will be listed. Summaries will be provided by treatment group for ITT population.

In addition, the following baseline characteristics will be summarized; ACLF grade, Ascites Grade, Ascites Refractory occurrences, Ascites Refractory Type, CLIF-C ACLF score, CLIF-C OF total score, Child-Pugh Score, MELD Score, country.

7.4 Medical History

Medical history terms are coded using the Medical Dictionary for Regulatory Activities (MedDRA) (version within one year of data base lock), associating lower-level terms with preferred terms (PTs) and system organ classes (SOCs). All medical history information will also be listed. A medical history summary will

Instituto Grifols, S.A. / Protocol IG1407

present the number/ percentage of subjects with at least one history event by treatment, SOC, and preferred term. Summaries will be provided by treatment group.

7.5 Disease History

Disease history including recent, recent abdominal ultrasound, and identification of cirrhosis etiology and the corresponding confirmation method of the cirrhosis will be listed and summarized by treatment group. Each subject may have more than one response selected for cirrhosis etiology; all recorded combinations will be included in the corresponding summary.

8 Treatments (PE-A 5%) and Other Medications

Unless otherwise noted, all listings and summaries of treatments and medications will be based on the Safety population.

8.1 Prior and Concomitant Medications

Summaries of all medications taken during the course of the study will be presented in tabular form and coded using Anatomical Therapeutic Chemical (ATC) classification codes via the World Health Organization Drug Classification Dictionary (WHO-DD), a version within one year of the data base lock will be employed. All medications will be summarized by treatment and sorted alphabetically by medication class (i.e., ATC level 2) and medication sub-class (i.e., ATC level 4). If the ATC level 2 or 4 term is missing, the higher ATC level term will be used in the medication summary table and data listing.

All medications will be listed by subject, with prior/concomitant designation as defined in section [6.1.6](#). Prior and concomitant medications will be summarized in separate tables by treatment (including an overall summary for prior medications), medication class and medication subclass. At each level of summarization, a subject will be counted once per medication class or subclass. The concomitant medication summary tables are displayed by standard medical therapy for management of ACLF, intravenous Immunoglobulin (IVIG) after plasma exchange, and non-SMT other medications. Summaries will be provided by treatment group for safety population.

8.2 Blood Products

All blood products used will be listed by subject and summarized in separate tables by treatment. The summary includes, but not limited to the following parameters: category (Fresh Frozen plasma after PE session per protocol, SMT and other blood products), blood product type and amount. At each level of summarization, a subject will be counted once per category and blood product type. Summaries will be provided by treatment group for safety population.

8.3 Extent of Exposure to PE-A 5%

For subjects randomized to SMT+PE-A 5%, all exposure details will be listed by visit.

An overall summary of exposure will present the duration of exposure (days), total volume of Albumin 5% exchanged (mL) and number of subjects who missed any scheduled treatment with PE-A 5% per protocol. Duration of exposure in days is defined as (date of last PE-A 5% – date of first PE-A 5% + 1). Interruptions, dose changes, and compliance are not considered in the calculation of duration of exposure.

Exchange interruptions will be summarized by visit. Number of exchanges, number and percentage of exchanges with interruptions, and number and percentage of exchanges with interruptions due to TEAE will be summarized.

8.4 Treatment Compliance

Instituto Grifols, S.A. / Protocol IG1407

Treatment compliance, plasma exchange (PE) compliance, and overall compliance will be listed and summarized for the SMT+PE-A 5% group specific to the PE-A 5% study drug treatment. In addition, the number and percentage of subjects with PE-A 5% compliance <80%, 80% to ≤120%, and >120% will be presented.

PE compliance will be calculated as (number of actual plasma exchanges / number of plasma exchanges expected or planned) *100. The expected number of exchanges be calculated as:

Expected exchanges = (Duration of exposure in days /2) + 1*

* The treatment schedule consists of 2 initial PE-A 5% sessions on consecutive days followed by every other day therefore the +1 takes the initial exchange into account

The maximum number of PE-A 5% exchanges permitted per the protocol is 9 with the last exchange scheduled to occur on treatment day 16. If the number of days on treatment is greater than 16 days, the number of expected exchanges will be 9.

The expected exchange integer value is obtained using the SAS 'Floor' function.

Treatment compliance will be calculated as (total volume exchanged/ total volume dispensed) *100. Missing visits will be excluded in the calculation.

Overall compliance will be calculated as (treatment compliance * PE compliance)/100.

Treatment compliance for the SMT alone group is not applicable for any PE-A 5% study drug compliance assessments.

9 Efficacy Analysis

All Efficacy listings and summaries will be based on the ITT population. In addition, the primary efficacy summaries and analyses will be repeated for the PP population.

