5.3.2 Discontinuation of Subjects from Treatment

If a subject receives a liver transplant, study treatment and all treatment related assessments will be discontinued upon transplant. The criteria to determine when a subject becomes a candidate for liver transplantation is described in [Section 5.3.2.1](#). The subject will continue to have Days 21, 28, 60, and 90 follow-up procedures performed.

Adverse events that will determine a subject’s discontinuation from study treatment include the following:

- New septic shock with norepinephrine requirements >0.5 mcg/kg/min
- Severe bleeding (gastrointestinal or other)
 - Any intracranial bleeding (excluding microhemorrhages <10 mm evident only on gradient-echo MRI)
 - Clinically overt signs of hemorrhage associated with a drop in hemoglobin of ≥5 g/dL, or a ≥15% absolute decrease in hematocrit, or requirement of ≥4 U of blood
 - Fatal bleeding (bleeding that directly results in death within 7 days)
- Anaphylactic shock or severe transfusion-related acute lung injury (TRALI) defined as new acute lung injury (ALI)/ARDS characterized by sudden development of dyspnea, bilateral infiltrates in chest X-ray, moderate or severe hypoxemia (PaO2/FiO2 < 200) with or without hypotension, and fever that develop during or within six hours after blood product administration
- Any other severe AEs (ie, acute myocardial infarction, cerebral hemorrhage, or intestinal necrosis) that preclude the continuation of the subject in the trial

Subjects with any one of these severe AEs will be discontinued from study treatment and all treatment-related assessments, and should continue to have subsequent planned visit assessment procedures performed.

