		
description of summary tables to be presented.
 
9. Section 7.3: Added ACLF grade, Ascites Grade, Ascites, Refractory occurrences, Ascites Refractory Type, CLIF-C ACLF score, CLIF-C OF total score, Child-Pugh Score, MELD score, and country to baseline characteristics summary. Removed ACLF-AD score.
 
10. Section 8.1: Displayed concomitant medication summary tables by three medications.
 
11. Section 8.2: Removed "time since the start of use" from summary. Used safety population for analysis.
 
12. Section 8.4: Added expected exchange number formular since site didn't always collect that information in CRF.
 
13. Section 9.1/9.2/9.4: Updated Efficacy Analysis to add analysis period and cut-off dates for clarity.
 
14. Section 9.1.1: Provided a more detailed explanation of the endpoint, censoring, and analysis period.
 
15. Section 9.1.2: Updated Primary Analysis to detail the hypothesis test performed, included protocol details, and specified where

--	--	---

		
stratification factors are recorded (i.e., IWRS).
 
16. Section 9.1.3: Added sensitivity analysis to consider different censoring methods and use stratification factors collected in the electronic case report form (eCRF) if more than 3% of subjects.
 
17. Section 9.2: Provided a more detailed explanation of the endpoint, censoring, and analysis period. Added sensitivity analysis for different censoring methods.
 
18. Section 9.3.1: Updated censoring event definition. Added an additional subgroup analysis for region in Exploratory Subgroup Analysis.
 
19. Section 9.3.2: Updated independent variables in the analysis model and specified the visits included in the analysis.
 
20. Section 9.3.3: Updated analysis method to use MMRM for change from baseline and specified visits included in the analysis.
 
21. Section 9.3.4: Updated analysis method to use MMRM for change from baseline, specified visits included, and added imputation rule for MELD score (how to

--	--	---

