- Subjects with partial response after the first 4 PE-A 5% sessions (reduction of 1 organ failure or more to ACLF-1b or ACLF-2) will be treated accordingly: as described below:
 - Subjects with partial response who in the course of the additional PE-A 5% sessions show complete response will receive 2 consolidating sessions after achieving complete response. See Table 4-2 for details.
 - Subjects with partial response who in the course of the additional PE-A 5% sessions worsen to ACLF-3b will be discontinued for the PE-A 5% sessions.
- In summary, regardless of the type of response, the total number of sessions should never be lower than 4 or higher than 9.

IVIgs will be administered intravenously at a dose of 200 mg/kg 1 day after every 2 PE-A 5% sessions in order to prevent the development of hypogammaglobulinemia and infection. In those subjects receiving an odd number of PE-A 5% sessions (e.g., #5, #7, or #9 PE-A 5% sessions when they are the last PE session for the subject), IVIGs will be administered 1 day after this PE-A 5% session at a dose of 100 mg/kg. Initial infusion rate of IVIGs will be of 0.5 mL/kg/hour, increasing to a maximum rate of 2 mL/kg/hour if tolerance is adequate. Refer Table [5-1](#) and Table [5-2](#) details.

Instituto Grifols, S.A. / Protocol IG1407

The entire study duration including follow-up period will be 90 days after randomization.

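### The SAP 8.4 exchange-compliance formula applies the maximum of 9 sessions but not the minimum of 4, so it detects gaps between sessions but not early stopping

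*SAP*

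**What the plan says.** SAP 8.4 defines PE compliance as actual exchanges over expected exchanges, times 100. The expected number is "Expected exchanges = (Duration of exposure in days /2) + 1", taken down to an integer, and is fixed at 9 when treatment runs beyond 16 days. The duration comes from SAP 8.3: "Duration of exposure in days is defined as (date of last PE-A 5% – date of first PE-A 5% + 1". It therefore runs to the last session given, not the last session due.

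The regimen in SAP 5.3.1 has two bounds: "the total number of sessions should never be lower than 4 or higher than 9". Sessions fall on Days 1, 2, 4, 6 and so on to Day 16, and the response to treatment decides how many are given (SAP Tables 5-1 and 5-2).

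The SAP version history (version 2.0, item 12) gives the origin of the formula: "Added expected exchange number formular since site", continuing that sites had not always captured the number on the CRF. It is a stand-in for a planned count that is not reliably recorded.

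SAP 8.4 also defines treatment compliance (volume exchanged over volume dispensed, leaving out missing visits) and overall compliance (the product of the two, divided by 100). It then bands compliance at below 80%, 80% to 120%, and above 120%.

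**The concern.** A compliance figure should compare what was given with what was due. Here the denominator is built from the subject's own last session, so it shrinks when the course is cut short. One planned number applies to every subject in the PE arm whatever the response, the minimum of 4, and it is left out, while the maximum of 9 is coded.

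At stake is how the delivered intervention is described. A subject who had one session and a subject who completed the course can both show 100%. The other measures do not correct this: treatment compliance adds no penalty for sessions never started, and overall compliance inherits both gaps. In an open-label trial that ended early, readers will want to know how much exchange was delivered, and this table is one place they will look.

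**Working it through.** **Inputs.** Planned session days 1, 2, 4, 6, 8, 10, 12, 14, 16 (SAP 5.3.1, Tables 5-1 and 5-2); minimum 4 and maximum 9 sessions (SAP 5.3.1); duration D = last session day − first session day + 1 (SAP 8.3); expected E = floor(D/2 + 1), set to 9 if D > 16 (SAP 8.4); PE compliance = 100 × sessions given / E.

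**The plan's own figure.** For a full course D = 16, so E = floor(16/2 + 1) = 9. This matches the SAP's maximum of 9 with the last session on Day 16.

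**With and without the minimum.** The last two columns use E = min(9, max(4, floor(D/2 + 1))).

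| Sessions given (days) | D | E, SAP | PE compliance, SAP | E with minimum | PE compliance with minimum |
|---|---|---|---|---|---|
| 1 (1) | 1 | floor(1.5) = 1 | 100% | 4 | 25% |
| 2 (1, 2) | 2 | floor(2) = 2 | 100% | 4 | 50% |
| 3 (1, 2, 4) | 4 | floor(3) = 3 | 100% | 4 | 75% |
| 4 (1, 2, 4, 6) | 6 | floor(4) = 4 | 100% | 4 | 100% |
| 9 (all planned days) | 16 | floor(9) = 9 | 100% | 9 | 100% |
| 2, one-day slip (1, 3) | 3 | floor(2.5) = 2 | 100% | 4 | 50% |
| 3, one-day slip (1, 2, 5) | 5 | floor(3.5) = 3 | 100% | 4 | 75% |
| 2, two-day slip (1, 4) | 4 | floor(3) = 3 | 66.7% | 4 | 50% |
| 3, two-day slip (1, 2, 6) | 6 | floor(4) = 4 | 75% | 4 | 75% |
| 8 of 9, one interior session missed | 16 | floor(9) = 9 | 88.9% | 9 | 88.9% |

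For every on-schedule course of 1 to 9 sessions, E equals the number given. The formula responds to gaps (66.7%, 75%, 88.9%) but not to an on-schedule stop. A single session always scores 100%, because D is then 1.

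**Overall compliance.** If volume compliance is 100%, an on-schedule stop after 1, 2 or 3 sessions also has overall compliance of 100 × 100 / 100 = 100%. With the minimum it is 25%, 50% or 75%.

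**What the minimum does not reach.** Take a partial responder who first achieves complete response at session 5. SAP Table 5-2 calls for 7 sessions. If that subject stops after 5 on schedule, E = 5 under either rule and compliance is 100%, against 5/7 = 71.4% of the sessions due.

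**The case against.** The strongest reply is that stopping before session 4 is often not non-compliance. Transplant ends treatment, and under Protocol 5.3.2 subjects with any of the listed severe adverse events "will be discontinued from study treatment and all treatment-related assessments, and should continue to have subsequent planned visit assessment procedures performed". Some subjects will die. For all of these, 100% of the sessions due while on treatment is a defensible description. This stands, and it is why the fix shows them separately. It does not rescue the formula, which gives the same 100% to a subject who stops before session 4 for any other reason. Mandated stops later in the course, where partial responders "worsen to ACLF-3b will be discontinued for the PE-A 5% sessions", come after session 4 and are not affected by the minimum.

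A second reply is that early stopping can be seen elsewhere, and much of this is right. SAP 8.3 summarizes exposure duration, where 1, 2 or 4 days reveals an on-schedule early stop, lists exposure by visit, and plans the "number of subjects who missed any scheduled treatment with PE-A 5% per protocol". SAP 7.2 lists protocol deviations and summarizes the major and critical ones. SAP 10.1 counts TEAEs leading to drug withdrawal. Protocol 6.3 requires reasons for giving less than the full prepared dose to be recorded. A reader might infer that early stopping is hidden, and the documents do not support that. The visibility is partial, though: SAP 8.3 does not say whether sessions never reached after a stop count as missed, it plans no per-subject distribution of sessions, and SAP 7.1 covers only leaving the study ("The number and percentage of subjects in the ITT population who discontinue from the study will be summarized by reason for discontinuation").

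A reader might also infer that early stoppers will certainly fall in the 80% to 120% band. SAP 8.4 does not say which of its three measures is banded. If it is overall compliance, the band also depends on volume.

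**Conclusion.** The formula is wrong as written for a regimen with a stated minimum. On-schedule stops after 1, 2 or 3 sessions score 100% instead of 25%, 50% or 75%, and a one-day slip in a two- or three-session course still scores 100%. This follows from the SAP's definitions and needs no outside assumption. The 25%, 50% and 75% take the minimum of 4 as the number due, and would be lower still for a subject whose response called for more.

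Severity is minor. Only the descriptive PE and overall compliance summaries are affected, and the bands if PE compliance is the measure banded. A reader might infer an effect on the efficacy result or the per-protocol set. There is none: per-protocol membership (SAP 6.4.3) rests on the first two sessions and the absence of major violations, and compliance enters no test.

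A reader might also try to size the problem from early mortality. The documents do not support that. A subject who died after receiving every session due is not a non-complier, deaths before the first session fall outside the Safety population on which this table is based, and the planned 190 per arm is not the enrolment of a trial that ended early. No rate is given for other early stops, so the number of subjects misclassified is unknown.

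**What to change.** In SAP 8.4, set expected exchanges to min(9, max(4, floor(duration/2 + 1))) and state which of the three measures is banded. Report subjects who stopped before session 4 because of death, transplant or a Protocol 5.3.2 event in a separate row, so that they are not read as non-compliant.

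In SAP 8.3, add the distribution of sessions received, 1 to 9. The minimum alone does not detect a stop after session 4 by a subject who needed 5 to 9.

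The cost is a few lines of programming and one frequency table. Exchange dates, deaths, transplants and the action taken with study product for adverse events are already collected. On-schedule courses of 4 to 9 sessions keep their 100%, and the only downside is a less favourable figure. If the tables have already been run, SAP Section 2 allows the revised summary to be documented as an unplanned analysis in the study report. At the least, a footnote should say that expected exchanges are counted only to the last session given.
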